### Rationale

The combination of mitoxantrone and etoposide is an active regimen in refractory/relapsed AML patients. In a retrospective study, we evaluated the efficacy and toxicity of mitoxantrone and etoposide in AML patients treated at our institution who did not respond to first induction therapy with cytarabine and an anthracycline. A total of thirty-five AML patients were treated with mitoxantrone (10 mg/m^2/d) on days 1-5 and etoposide (100 mg/m^2/d) on days 1-5. Thirteen of thirty-five patients (37%) achieved CR. There were no grade 3/4 hepatic toxicities. The median duration of neutropenia in patients achieving CR was 29 days after reinduction. 14% of patients died from infectious complications.

In order to increase the efficacy of mitoxantrone and etoposide as second line therapy in patients with AML we propose to conduct a phase II clinical trial evaluating the safety and efficacy of the combination of GO, mitoxantrone and etoposide. A similar trial was open in our institution before Pfizer withdrew the drug from the market in 2010^26. Before the withdrawal 5 patients were treated with a regimen consisted of mitoxantrone 10 mg/m^2 administered intravenously on days 1–3, etoposide 100 mg/m^2 administered on days 1–5 and on day 6 GO 3 mg/m^2. Three of the five patients achieved a CR. There were no treatment-related deaths. All patients developed grade 3–4 neutropenia and thrombocytopenia, with complete responders requiring a median of 19 days (range, 17–34 days) from the completion of

treatment to recover their neutrophils and a median of 24 days (range, 17–34 days) to recover their platelets. One patient developed grade 3 ALT transaminitis that resolved within 24 h and one patient developed a transient ischemic attack. No patient developed clinical signs or symptoms of veno-occlusive disease.

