### **5.3. Study design**

**5.3.1 Definition of complete remission (CR):** An evaluable patient will be classified as having complete remission if they meet the criteria in Appendix II.

**Decision Rule (Simon two-stage design):** The largest CR rate where the proposed treatment regimen would be considered ineffective in this population is 35%. Subsequent studies will be warranted if the CR rate is 50% or higher or the CR rates are similar to historical data but

the disease-free survival and the overall survival are improved in comparison to our institution's historical cohort. The following optimal Simon two stage design uses 44 patients to test the null hypothesis that the true CR rate in the given patient population is at most 35%.

**Stage 1:** Enter 16 evaluable patients. If 5 or fewer patients have a CR in this timeframe, we will consider this early evidence that this treatment regimen is not sufficiently efficacious in this patient population, and the accrual of patients will be stopped. If 6 or more patients have a CR, then accrual will continue in the second stage of this trial.

**Stage 2:** Enter an additional 28 evaluable patients to the trial. If 19 or more patients achievea complete remission, the treatment will be promoted for further consideration. This design has  $\alpha=0.15$  and  $\beta=0.20$ ; the large value of  $\alpha$  is appropriate in an early phase trial. If the probability of CR is 35%, the expected sample size is 30.3 patients, i.e., the probability that the trial will be halted after 16 patients is 48.9%.

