### **5.3.2 Monitoring for treatment-induced mortality**

The trial will be continually monitored to ensure that treatment-induced mortality is not excessive, defined as  $>0.20$  of patients treated. A safety-evaluable patient is a patient

who was consented and started the protocol chemotherapy. All safety-evaluable patients, not just those evaluable for clinical response, are counted in the interim analysis for mortality. The cutpoints are listed in Table 2.

**Table 2.** Stopping rule for excessive mortality. The trial will be halted if, for the number of patients in the following table, the number of deaths is greater than or equal to the given number.

# Patients	# Deaths	# Patients	# Deaths
4	3	24	7
6	3	26	8
8	3	28	8
10	4	30	8
12	4	32	9
14	5	34	9
16	5	36	10
18	6	38	10
20	6	40	11
22	7	42	11

Justification of the stopping rule: It was assumed that under standard of care, the probability of death is  $\pi=0.2$ . A beta-binomial model is assumed with  $\alpha=2$  and  $\beta=8$ . If the number of deaths,  $x$ , is greater than the value in the Stopping Rule table for the number of patients,  $n$ , then:

$$P(\pi>0.2|\alpha,\beta,x,n)>0.75.$$

Under different assumptions of the true probability of death (True P(Death)), the expected number of patients ( $E(n)$ ) and the probability of the trial stopping early ( $P(Stop Early)$ ) were determined by Monte Carlo simulation:

True P(Death)	E(n)	P(Stop Early)
0.20	28.3	0.513
0.25	22.9	0.720
0.30	15.8	0.900
0.35	11.5	0.973
0.40	8.4	0.994
0.45	6.9	0.996

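### The α and β in section 5.3.1 describe the Simon CR rule alone; the plan gives no operating characteristics for that rule and the Table 2 mortality rule acting together

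*Combined protocol and SAP*

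**What the plan says.** Section 5.3.1 sets the null rate: "The largest CR rate where the proposed treatment regimen would be considered ineffective in this population is 35" per cent. It sets the target as follows: "Subsequent studies will be warranted if the CR rate is 50% or higher". Stage 1 takes 16 evaluable patients and stops at 5 or fewer CRs. Stage 2 adds 28, and 19 or more CRs among the 44 lead to promotion. The section then states: "This design has $\alpha=0.15$ and $\beta=0.20$ ; the large value of $\alpha$ is appropriate in an early phase trial". It adds an expected sample size of 30.3 and an early-stop probability of 48.9% when the CR rate is 35%.

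Section 5.3.2 adds a second rule on all patients who start protocol chemotherapy, in which deaths are compared with a tabled cutpoint: "The trial will be halted if, for the number of patients in the following table, the number of deaths is greater than or equal to". Looks run from 4 to 42 patients. Excessive mortality is defined as above 0.20. On the benchmark the section says: "It was assumed that under standard of care, the probability of death is" 0.2. Its operating-characteristics table starts at a true death rate of 0.20, where it gives a stopping probability of 0.513. There is no row below that.

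On the same mitoxantrone-etoposide backbone without GO, the Rationale in section 1.2 reports that "14% of patients died from infectious complications", from a retrospective series of 35.

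**The concern.** Both rules govern the same trial. A trial halted under Table 2 does not reach the 44 evaluable patients that the promotion rule needs, so the 80% in section 5.3.1 is conditional on the mortality rule staying silent. A reader who takes it as the chance that this trial will promote a regimen with a 50% CR rate will be too optimistic by an amount that depends on the true death rate. The plan does not let the reader work that amount out for any death rate inside its own acceptable range. The expected sample size and early-stop figures are likewise those of the CR rule only.

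**Working it through.** **Inputs.** CR rates 0.35 and 0.50, and boundaries 5/16 and 19/44 (section 5.3.1). Table 2 cutpoints at n = 4, 6, …, 42, halting when deaths reach the tabled number (section 5.3.2). Death rates: 0.20 from section 5.3.2; 14% from section 1.2, taken as 5/35 = 0.143; 0.05 and 0.10 as illustrations. The plan does not say how deaths relate to CR, so two models are used as assumptions: (a) deaths independent of CR; (b) every death is an evaluable non-responder, with the overall CR rate held at 50%.

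**Step 1: the CR rule alone.** P(promote) = Σ over x = 6 to 16 of Bin(x; 16, p) × P[Bin(28, p) ≥ 19 − x].
- p = 0.50: 0.8015, so β = 0.1985.
- p = 0.35: 0.142, within the stated 0.15.
- Early stop at p = 0.35: P[Bin(16, 0.35) ≤ 5] = 0.490, against 48.9% stated.
- Expected N = 16 + 28 × (1 − 0.490) = 30.28, against 30.3 stated.

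The section 5.3.1 figures reproduce.

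**Step 2: both rules together.** An exact recursion over patients, CRs and deaths applies Table 2 at each listed n, the CR rule at 16 and the promotion rule at 44. Under model (a) it reduces to a product, P(promote) = 0.8015 × [1 − P(Table 2 halts)]:
- 5/35: 0.8015 × (1 − 0.173) = 0.663
- 0.20: 0.8015 × (1 − 0.438) = 0.450 (0.451 in the table, where the unrounded value is 0.4505)

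Model (a) gives the same answer if deaths are unevaluable and replaced without limit.

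| True death rate | Table 2 halt (alone, to 44) | Promote, model (a) | Promote, model (b) |
|---|---|---|---|
| 0.05 | 0.007 | 0.796 | 0.797 |
| 0.10 | 0.058 | 0.755 | 0.766 |
| 5/35 | 0.173 | 0.663 | 0.692 |
| 0.20 | 0.438 | 0.451 | 0.500 |

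**Step 3: false promotion.** At a true CR rate of 35% the chance of promotion falls from 0.142 to 0.118–0.131 at 5/35 and to 0.080–0.108 at 0.20. α stays below 0.15.

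**Step 4: sensitivity.**
- *Reading of Table 2.* The caption halts at or above the tabled number; the justification below it speaks of exceeding that number. Under the second reading, promotion is 0.756–0.771 at 5/35 and 0.610–0.657 at 0.20. The stated Beta(2, 8) posterior fits the caption: at every tabled cutpoint P(π > 0.2) exceeds 0.75, and with one death fewer it is below 0.75.
- *53-patient cap.* Section 5.2.1 lists death among the reasons for being unevaluable and caps enrolment at 53. If every death is unevaluable and replaced within that cap, promotion is 0.57 at 5/35 and 0.25 at 0.20. Much of that drop comes from the cap: at 0.20, the cap without Table 2 would already give 0.29.
- *The plan's own stopping figure.* The 0.513 at a death rate of 0.20 does not reproduce from Table 2: the exact value is 0.438, or about 0.47 with a look after every patient up to 44. Using 0.513 would give 0.8015 × 0.487 = 0.39.

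**The case against.** The strongest reply is that nothing in the quoted sentence is false. It describes the Simon design just set out, its figures are right for that design, and quoting Simon error rates for the efficacy rule alone is common practice. A halt for deaths is the intended action of a separate rule and not a type II error of the CR test. Section 5.2.1 makes the 44-patient maximum subject to toxicity, and section 5.3.2 already shows that about half of trials would stop at a death rate of 0.20. All of this stands. A reader might infer that β = 0.20 is miscalculated; the documents do not support that.

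A reader might also infer that the protocol expects mortality of 14% to 20%. It does not say so. The 14% is infectious deaths in a retrospective cohort without GO, and 0.20 is a standard-of-care benchmark at the edge of the excessive range. The five earlier patients given GO with these drugs had no treatment-related deaths, although five patients on a shorter mitoxantrone schedule cannot exclude 14%. At death rates of 5% to 10% the loss is only about 0.5 to 5 points.

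Finally, section 5.3.1 allows a second route to further study, through improved survival at a CR rate similar to historical data. That route is not modelled here.

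What remains is that no joint figure is given, and that no halting probability is given for any death rate the protocol itself regards as acceptable.

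**Conclusion.** The point holds as a reporting gap, not as an arithmetic error. Section 5.3.1 is right for the CR rule alone. With both rules in force and Table 2 read as its caption is printed, a regimen with a true CR rate of 50% reaches promotion through 19/44 with probability about 0.80 at a 5% death rate, 0.76–0.77 at 10%, 0.66–0.69 at 5/35 and 0.45–0.50 at 0.20. At 5/35, which is acceptable by the protocol's definition, Table 2 halts about 17% of trials, and the plan does not say so. α is not inflated.

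A reader might infer that the trial's true power is 0.66, or 0.45. The documents do not support either single value. The result depends on the unknown death rate, on the unstated relation between death and CR, on which of the two wordings in section 5.3.2 applies, and on how the 53-patient cap treats deaths.

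**What to change.** - In section 5.3.1, state that α and β, with the expected sample size and early-stop probability, apply to the CR rule if the mortality rule does not halt the trial.
- Add a joint operating-characteristics table: true CR rates of 35% and 50% crossed with death rates from 0.05 to 0.25. Give the probabilities of promotion, futility stop and mortality halt, and the expected N. State the death model, the reading of Table 2 and the handling of the 53-patient cap beside the table.
- In section 5.3.2, reconcile the caption with the justification. Then recompute the whole operating-characteristics table, including rows below 0.20. Adding rows to the existing table would not be enough, because its 0.513 does not reproduce.
- Do not enter a single overall power value.

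The cost is a short calculation, one new table, one recomputed table and a few sentences. Neither CR boundary changes, nor do the tabled mortality cutpoints or the sample size. The downside is that the stated power will look less favourable.

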### **5.3.2 Monitoring for treatment-induced mortality**

The trial will be continually monitored to ensure that treatment-induced mortality is not excessive, defined as  $>0.20$  of patients treated. A safety-evaluable patient is a patient

who was consented and started the protocol chemotherapy. All safety-evaluable patients, not just those evaluable for clinical response, are counted in the interim analysis for mortality. The cutpoints are listed in Table 2.

**Table 2.** Stopping rule for excessive mortality. The trial will be halted if, for the number of patients in the following table, the number of deaths is greater than or equal to the given number.

# Patients	# Deaths	# Patients	# Deaths
4	3	24	7
6	3	26	8
8	3	28	8
10	4	30	8
12	4	32	9
14	5	34	9
16	5	36	10
18	6	38	10
20	6	40	11
22	7	42	11

Justification of the stopping rule: It was assumed that under standard of care, the probability of death is  $\pi=0.2$ . A beta-binomial model is assumed with  $\alpha=2$  and  $\beta=8$ . If the number of deaths,  $x$ , is greater than the value in the Stopping Rule table for the number of patients,  $n$ , then:

$$P(\pi>0.2|\alpha,\beta,x,n)>0.75.$$

Under different assumptions of the true probability of death (True P(Death)), the expected number of patients ( $E(n)$ ) and the probability of the trial stopping early ( $P(Stop Early)$ ) were determined by Monte Carlo simulation:

True P(Death)	E(n)	P(Stop Early)
0.20	28.3	0.513
0.25	22.9	0.720
0.30	15.8	0.900
0.35	11.5	0.973
0.40	8.4	0.994
0.45	6.9	0.996

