## **5.0 STATISTICAL CONSIDERATIONS AND METHODOLOGY**

### **5.1 Number and evaluable of patients**

This is a phase II study of the combination therapy of GO, mitoxantrone and etoposide as second line therapy in patients with acute myeloid leukemia. The study is designed to assess the therapeutic efficacy and the toxicity profile using Simon's optimal two-stage phase II design to permit early stopping of the trial if there is strong evidence that the studied treatment is ineffectual.

To be evaluable for clinical response, a patient must:

1. Receive a total of 5 days of mitoxantrone and etoposide,
2. Receive 1 dose of GO and
3. Have a follow-up bone marrow biopsy to evaluate the response to therapy.

Additional participants will be recruited to replace those who are not evaluable for clinical response. The accrual target is a maximum of 44 response-evaluable patients. All participants who begin treatment will be counted in the interim analysis for excess mortality.

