### **5.2. Sample Size/Accrual rate**

#### **5.2.1 Sample size**

This study is expected to require a minimum of 16 patients (at the interim evaluation of response) and a maximum of 44 response-evaluable patients unless undue toxicity is encountered. We anticipate accruing up to 9 additional patients (~20%) to account for patients who may prove unevaluable (i.e. ineligibility, cancellations, death or major violations). Therefore, our overall sample size will be a maximum of 53 patients.

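### The stated E(n) and P(Stop Early) for the mortality stopping rule are not those of Table 2 as printed

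*Combined protocol and SAP*

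**What the plan says.** Section 5.3.2 opens with a commitment to ongoing review: "The trial will be continually monitored to ensure that treatment-induced mortality is not excessive". Excessive means a proportion above 0.20. The Table 2 caption then gives the operative rule. The trial halts if, "for the number of patients in the following table, the number of deaths is greater than or equal to the given number". The rows are the even numbers from 4 to 42.

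The justification takes a Beta(2,8) prior on the death probability π. It says that the posterior probability of π > 0.2 exceeds 0.75 when the death count "is greater than the value in the Stopping Rule table for the number of patients". Six rows of E(n) and P(Stop Early) follow, for true death probabilities from 0.20 to 0.45; these "were determined by Monte Carlo simulation". The number of runs, the look schedule and the maximum n are not stated.

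On numbers treated, section 5.1 says "The accrual target is a maximum of 44 response-evaluable patients" and "All participants who begin treatment will be counted in the interim analysis for excess mortality". Section 5.2.1 adds up to nine places and concludes that "our overall sample size will be a maximum of 53 patients". The extra places cover "ineligibility, cancellations, death or major violations", so 53 is an upper bound on the number who start treatment.

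**The concern.** Table 2 is the protocol's only numerical boundary for mortality, and the six rows are what a reviewer has for judging how it performs. If they belong to another rule, readers are misinformed about the chance of a false stop at the assumed standard-of-care rate, the chance of stopping when mortality is excessive, and the number treated before a stop.

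The section also leaves three things to interpretation: whether looks fall only at the listed even numbers or after every patient, whether the boundary is ≥ or >, and what applies after patient 42. With three deaths among five patients, for example, the monitoring group has no printed row to apply.

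**Working it through.** **Inputs (section 5.3.2).** Prior Beta(2,8); criterion P(π > 0.2) > 0.75; the 20 cutpoints of Table 2; the six stated rows. Only the mortality rule is modelled, because the plan's rows vary only the death probability.

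**Step 1: are the cutpoints right?** After x deaths in n patients the posterior is Beta(2+x, 8+n−x). For whole-number parameters, P(π > 0.2) equals the probability that a Binomial(n+9, 0.2) count is at most x+1.

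- n=4: x=3 gives 0.901, x=2 gives 0.747. The cutpoint is 3, as printed.
- n=8: x=3 gives 0.758, x=2 gives 0.549. The cutpoint is 3, as printed.

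Over all 20 rows, the posterior at the tabled count is at least 0.758 (n=8), and at one death fewer it is at most 0.747 (n=4). Every tabled number is therefore the smallest count that meets the criterion. The caption's ≥ is right. The justification's greater than is true as an implication but does not define the boundary.

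**Step 2: operating characteristics of the printed rule.** Let f_n(x) be the probability of x deaths in n patients without having stopped. Then f_n(x) = (1−p)·f_{n−1}(x) + p·f_{n−1}(x−1). At each listed n, the mass with x ≥ cutpoint is removed and added to P(stop), and n times that mass is added to E(n). Mass remaining at 42 is counted at n=42. This is exact.

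| True rate | E(n) stated | E(n) exact | Gap | P(stop) stated | P(stop) exact | Gap |
|---|---|---|---|---|---|---|
| 0.20 | 28.3 | 30.13 | +1.83 | 0.513 | 0.438 | −0.075 |
| 0.25 | 22.9 | 23.23 | +0.33 | 0.720 | 0.692 | −0.028 |
| 0.30 | 15.8 | 17.20 | +1.40 | 0.900 | 0.872 | −0.028 |
| 0.35 | 11.5 | 12.81 | +1.31 | 0.973 | 0.960 | −0.013 |
| 0.40 | 8.4 | 9.95 | +1.55 | 0.994 | 0.991 | −0.003 |
| 0.45 | 6.9 | 8.15 | +1.25 | 0.996 | 0.998 | +0.002 |

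The plan's figures are not reproduced. A maximum of 44 widens the E(n) gap at 0.20 to 31.26 − 28.3 = 2.96. Reading the rule with > moves further away: P(stop) at 0.20 becomes 0.238.

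**Step 3: could it be simulation error?** Suppose all six rows used the same number of runs R. Each stated probability must then be a multiple of 1/R rounded to three decimals. No R below 478 satisfies all six (500 also fails; 700, 800 and 1,000 work). At R=478:

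- P(stop) at 0.20: standard error √(0.438 × 0.562 / 478) = 0.0227; 0.075 / 0.0227 = 3.3 standard errors.
- E(n) at 0.45: the stopping time has standard deviation 5.29, so the standard error is 5.29 / √478 = 0.242; 1.25 / 0.242 = 5.2 standard errors.

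At an assumed 1,000 runs these become 4.8 and 7.5. Simulation error is not a sufficient explanation at the printed looks.

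**Step 4: a different look schedule.** Applying the same criterion after every patient from n=2 to 44 gives, in row order, 29.7/0.471, 22.1/0.721, 15.8/0.890, 11.3/0.968, 8.5/0.993 and 6.6/0.999. This is closer to the stated figures, but it needs looks at odd n and at n=2 and 3, which Table 2 does not print.

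**Step 5: the end of the table.** Adding the criterion's value at n=44 (12 deaths) raises P(stop) by 0.1, 0.3 and 0.3 points at 0.20, 0.25 and 0.30. Extending even looks to 52, with 53 treated, raises it by 3.2, 5.0 and 4.0 points.

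**The case against.** The strongest reply is that the section promises continual monitoring and states the criterion in full, so Table 2 can be read as an abbreviated listing of a rule applied after every patient. On that reading, with looks from n=2, a maximum of 44 and about 478 runs, all twelve stated figures lie within about 2 standard errors, and a small simulation could account for the differences.

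This is a plausible account of where the figures came from, but it does not make them the figures of the printed rule. It depends on unprinted looks at n=2 and 3. If looks after every patient begin at the first printed row, n=4, then E(n) at 0.20, 0.40 and 0.45 still misses by 3.3 to 3.6 standard errors at 478 runs. With looks from n=2 but 1,000 runs, the 0.20 row is 2.6 standard errors off. The documents do not settle it.

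Several points on scale do stand:

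- At 478 runs the P(stop) gaps at 0.25 and 0.30 are only 1.3 and 1.8 standard errors, and E(n) at 0.25 is indistinguishable from noise. The firm evidence of mismatch is P(stop) at 0.20 and E(n) at 0.20 and at 0.30 to 0.45.
- The largest gap is at 0.20, where mortality is not excessive by the plan's definition. There the stated figure overstates false stopping and does not hide a safety failure.
- The inequality wording is editorial, since the caption is operative and correct.
- The table ending at 42 matters little: the criterion yields a value at any n, and section 7 lets the DSMB and DSMC suspend accrual.

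**Conclusion.** The concern holds. The stated E(n) and P(Stop Early) are not those of Table 2 applied with ≥ at its listed patient numbers. The printed rule stops 7.5 points less often than stated at 0.20 and 2.8 points less often at 0.25 and 0.30. It treats 1.25 to 1.55 more patients on average at 0.30 to 0.45.

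The cutpoint check and the mismatch are exact, given a maximum of 42 and the caption read literally. Ruling out simulation error also assumes a common number of runs across the six rows. The cause of the stated figures is not established. No printed cutpoint is wrong and the effect is modest, so this should be fixed but does not undermine the trial.

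**What to change.** All changes are in section 5.3.2.

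1. In the justification, change greater than to greater than or equal to.
2. State the looks, so that continual monitoring and the even-n table agree. If the printed looks are kept, say so. If looks are after every patient, print the odd-n values from the same criterion (n:deaths): 5:3, 7:3, 9:4, 11:4, 13:5, 15:5, 17:6, 19:6, 21:6, 23:7, 25:7, 27:8, 29:8, 31:9, 33:9, 35:10, 37:10, 39:10, 41:11. Say also whether looks begin before n=4; the criterion gives 2 deaths at n=2 and n=3.
3. Extend the table with the plan's own criterion: 11 deaths at n=43, 12 at 44 to 48, 13 at 49 to 53.
4. Recompute E(n) and P(Stop Early) for exactly that schedule and maximum n. Give the number of simulations, or use the exact recursion.

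The cost is text and table edits, with no extra patients or data and no change to a printed cutpoint. Keeping the printed looks means reporting lower stopping probabilities (0.438, 0.692 and 0.872 at 0.20, 0.25 and 0.30 with maximum 42). Choosing looks after every patient raises the false-stop probability at 0.20 to 0.455 (from n=4) or 0.471 (from n=2), with maximum 44. That choice is the sponsor's.
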